2. LIST OF ABBREVIATIONS

AE Adverse Event

CA Competent Authority
CI Confidence Interval

COPD Chronic Obstructive Pulmonary Disease

ENCePP European Network of Centres for

Pharmacoepidemiology and Pharmacovigilance

GPP Good Pharmacoepidemiology Practice GVP Good Pharmacovigilance Practices

ICS Inhaled corticolsteroids

IEC Independent Ethics Committee
 IRB Institutional Review Board
 LABA Long-acting β2-agonists

LAMA Long-acting muscarinic antagonists
MAH Marketing Authorization Holder
NHI Taiwan National Health Insurance

NIS Non-Interventional Study

Olo Olodaterol

PASS Post-Authorization Safety Study

SAE Serious Adverse Event

Tio Tiotropium

NIS Protocol Page 6 of 48 BI Study Number: 1237-0110 c38660249-01

Proprietary confidential information © 2022 Boehringer Ingelheim International GmbH or one or more of its affiliated

4. ABSTRACT

COPD is a leading cause of morbidity and mortality throughout the world. Long-acting bronchodilator medications, which include long-acting β2-agonists (LABAs) and the long-acting muscarinic antagonists (LAMAs) such as tiotropium, are the central maintenance therapy to the management of COPD, with inhaled corticosteroids (ICSs) added with increasing severity. The up-to-date GOLD guideline recommends to initiate ICS/LABA in patients with high blood eosinophils level and frequent exacerbation history[P21-01394]. However, ICS containing therapy has been widely used inappropriately in real world practice.

The role of ICS in COPD has been debated for decades and studies have been conducted to investigate the effect of ICS-containing therapy in patients with COPD. INSPIRE [P07-11820] study indicated that ICS/LABA and tiotropium showed similar effects on the reduction of exacerbations, while the risk of pneumonia was higher in the ICS/LABA group. And the FLAME [P16-05628] study showed LAMA/LABA was superior to ICS/LABA in terms of exacerbation prevention, while in some newly published data focusing on FDC triple therapy showing reversed results.

With more and more fixed dose combination medications, i.e. LAMA/LABA, ICS/LABA/LAMA, approved and prescribed in recent years, it is of clinical interests to understand the effectiveness and safety profile of these therapies in real world settings.

The aim of this real world study is to assess effectiveness and safety profile between tiotropium/olodaterol (Tio/Olo) and ICS/LABA. The primary outcome of the study will be risk of moderate or severe COPD exacerbations. Other outcomes include time to ICS/LABA/LAMA escalation, rate of escalation to triple therapy, pneumonia and rescue medication use.

NIS Protocol Page 8 of 48 BI Study Number: 1237-0110 c38660249-01

Name of company:			
Boehringer Ingelhein	1		
Name of finished me product: Spiolto Respimat	edicinal		
Name of active ingre Tiotropium + Olodate {R03AL06}			
Protocol date:	Study number:	Version/Revision:	Version/Revision date:
23 May 2022	1237-0110	1.0	NA
Title of study:	Effectiveness of Maintenance Treatment with Tiotropium + Olodaterol in Comparison to Inhaled Corticosteroids + Long-acting β2 agonists in COPD patients in Taiwan: a non-interventional study based on the Taiwan National Health Insurance (NHI) data		
Rationale and background:	world. Long-ac acting β2-agoni (LAMAs) such management of increasing seve initiate ICS/LA frequent exacer therapy has been conducted patients with Control ICS/LABA and exacerbations, which is group. And the superior to ICS some newly pureversed results. With more and LAMA/LABA, years, it is of claprofile of these. The aim of this rebetween tiotropic outcome of the strength in the superior of th	ling cause of morbidity and morting bronchodilator medication ists (LABAs) and the long-acting as tiotropium, are the central in a copposition of the control of the control of the copposition of the copp	s, which include longing muscarinic antagonists naintenance therapy to the croids (ICSs) added with deline recommends to eosinophils level and owever, ICS containing in real world practice. If decades and studies have S-containing therapy in study indicated that ects on the reduction of as higher in the ICS/LABA howed LAMA/LABA was on prevention, while in riple therapy showing medications, i.e. and prescribed in recent the effectiveness and safety so ectiveness and safety profile eS/LABA. The primary oderate or severe COPD

NIS Protocol Page 9 of 48 BI Study Number: 1237-0110 c38660249-01

Name of company:				
Boehringer Ingelheim	1			
Name of finished medicinal				
product:	Michigan			
Spiolto Respimat				
Name of active ingre Tiotropium + Olodate				
{R03AL06}	101			
(Rosando)				
Protocol date:	Study	Version/Revision:	Version/Revision date:	
	number:			
23 May 2022	1237-0110	1.0	NA	
	escalation, rate medication use	of escalation to triple therapy,	pneumonia and rescue	
Research question	Primary objecti	ive·		
and objectives:	•		ware CODD evacerbations	
	To compare time to the first moderate or severe COPD exacerbations between initiators of Tiotropium / Olodaterol (Tio/Olo) and inhaled			
	corticolsteroids / long-acting β2-agonists (ICS/LABA) after entry			
	between 1st January 2014 and 31st December 2019			
	Secondary objectives:			
	To compare time to escalation to triple therapy between initiators of Tio/Olo and ICS/LABA;			
	 To compare the rate of escalation to triple therapy between initiators of Tio/Olo and ICS/LABA; 			
	_	To compare the time to first hospitalization for community-acquired oneumonia between initiators of Tio/Olo and ICS/LABA;		
		npare the number of prescriptions of rescue medication between ors of Tio/Olo and ICS/LABA		
	To compare exacerbation	compare the annualized rate of moderate or severe COPD		
		l of between 1st January 2014 a	nd 31st December 2019	
		ry objectives above	nd 31st December 2017	
Study design:		e a non-interventional cohort st	tudy based on existing data	
	(NISed).			

NIS Protocol Page 10 of 48 BI Study Number: 1237-0110 c38660249-01

				
Name of company:				
Boehringer Ingelheim	1			
Name of finished me product: Spiolto Respimat	edicinal			
Name of active ingredient: Tiotropium + Olodaterol {R03AL06}				
(110011200)				
Protocol date:	Study number:	Version/Revision:	Version/Revision date:	
23 May 2022	1237-0110	1.0	NA	
Population:	Inclusion criter	ia:		
	LABA/ICS December 2	e prescription for Tio/Olo comb s combined inhaler between 1st J 2019. years on the index date		
	3. At least one date;	ne diagnosis of COPD at any time prior to or on the index ne year of continuous medical and health insurance plan prior ex date will be required to allow for a look-back period for lates and identification of new use of the study drugs; ne record in the health insurance system database;		
	to the index the covariat			
	Exclusion criter		system dadase,	
	Any use of or fixed for	LAMA/LABA, ICS/LABA, or rm for one year prior to the inde	ex date;	
		s with asthma, allergic rhinitis, l lung transplant identified at any	-	
Variables:	Exposures:			
variables.	Exposure of thi	Exposure of this study is defined as new initiation of Fiotropium/Olodaterol, or ICS/LABA during the study period. Outcomes: Primary outcome:		
	Outcomes:			
	• Time to the entry	e first moderate or severe CC	OPD exacerbations after	
	_	tcomes: ple therapy escalation after entry rate of triple therapy initiation;		

NIS Protocol Page 11 of 48 BI Study Number: 1237-0110 c38660249-01

			_
Name of company:			
Boehringer Ingelhein	ı		
Name of finished me product: Spiolto Respimat	edicinal		
Name of active ingredient: Tiotropium + Olodaterol {R03AL06}			
Protocol date:	Study number:	Version/Revision:	Version/Revision date:
23 May 2022	1237-0110	1.0	NA
	pneumonia; Annualized rate of prescriptions of rescue medication as: annualized rate=number of prescriptions/total patrisk=number of prescriptions per patient year); Annualized rate of moderate or severe COPD exacer (calculated as: annualized rate=number of moderate of COPD exacerbations/total patient year at risk=number exacerbations per patient year) Covariates: Demographic characteristics and cohort entry informations sex Age Calendar year of cohort entry Season of index date (winter, spring, summer, fall) Additional, the following clinical characteristics will be measured during the 1 year pre-index baseline period: Specific previous COPD treatments LAMA monotherapy LABA monotherapy LABA monotherapy LABA monotherapy LAMA/ICS combination therapy		ions/total patient year at t year); COPD exacerbation of moderate or severe at risk=number of http://doi.org/10.1001/

NIS Protocol Page 12 of 48 BI Study Number: 1237-0110 c38660249-01

Name of company:			
Boehringer Ingelheim			
Name of finished me product: Spiolto Respimat	dicinal		
Name of active ingre Tiotropium + Olodate {R03AL06}			
Protocol date:	Study	Version/Revision:	Version/Revision date:
23 May 2022	number: 1237-0110	1.0	NA
	Use of other re	espiratory drugs	
	Mucoly	tics	
	> Theophy	ylline	
	> Short-ac	eting beta-agonists	
	➤ Short-ac	cting muscarinic antagonists	
	both 12 m categorize All ex An or any fr an an Hosp prima diagn Number of	of hospitalizations caused by	ere) is code for COPD in ral corticosteroid or ions (Moderate) om visits with a
	> 0; > 1; > 2+;	12 months prior to the index of all-cause hospitalizations in e:	

NIS Protocol Page 13 of 48 BI Study Number: 1237-0110 c38660249-01

Name of company:			
Name of finished medicinal product: Spiolto Respimat			
Name of active ingre Tiotropium + Olodate {R03AL06}			
Protocol date:	Study	Version/Revision:	Version/Revision date:
	number:		
23 May 2022	1237-0110	1.0	NA
	 Cerel Diabe Chro Pneu Canc Cirrh Charlson History of or on the dispensing Cardinantian intrate heart Lipid Blood Antic Antic 	iovascular disease provascular disease etes nic kidney disease monia er osis Comorbidity Index (CCI) f medications dispensed in index date will be identifie g history: iovascular drugs: ypertensives rrhythmics tes failure medications d-lowering medications d glucose-lowering medicat coagulants and antiplatelet a piotics meoplastic agents	d from the pharmacy

NIS Protocol Page 14 of 48 BI Study Number: 1237-0110 c38660249-01

Name of company:			
Boehringer Ingelhein	1		
Name of finished me product: Spiolto Respimat	edicinal		
Name of active ingre Tiotropium + Olodate {R03AL06}			
Protocol date:	Study number:	Version/Revision:	Version/Revision date:
23 May 2022	1237-0110	1.0	NA
Data sources:	Data used in this study will come from the Taiwan National Health Insurance (NHI) claims data between 2014 and 2019. Data sources include Taiwan NHI, Taiwan cancer registry (TCR) and Taiwan Mortality Data. Taiwan Department of Statistics, Ministry of Health and Welfare is the unit designated by the government to manage health and social welfare statistical databases, and to develop data platform for academic research. Through the services provided by the Health and Welfare Data Science Center (HWDSC) of the Department of Statistics, researchers may access a wide range of health and welfare data, including claims, mortality (with cause of death) and Taiwan Cancer Registry (TCR). The HWDSC staff encrypt the national ID for all individuals according to a secure encryption algorithm that is not made known to the public. The encrypted ID is unique for all individuals and will be used for linkage between databases.		
	Taiwan Nation publicly funderesidents. Heat coverage is martaiwan contrataiwan to prolocations of heat Taiwan. Salar premium calcusocioeconomic Related Group	ional Health Insurance (NHI) started in 1995 and is a added single payer health insurance program for all fealth insurance for individuals is required by law and more than 99%. The majority of healthcare providers in tract with the National Health Insurance Agency in provide a wide range of medical services. Geographic health care claims are broadly classified into 6 regions in lary range, which serves as the basis for enrollees' alculation, can serve as a proxy indicator for mic status. Bundled payment according to the Diagnosistup system only applies in limited number of disease therefore detailed drug use information during	

NIS Protocol Page 15 of 48 BI Study Number: 1237-0110 c38660249-01

Name of company:			
Boehringer Ingelheim	1		
Name of finished me product: Spiolto Respimat	dicinal		
Name of active ingre Tiotropium + Olodate {R03AL06}			
Protocol date:	Study number:	Version/Revision:	Version/Revision date:
23 May 2022	1237-0110	1.0	NA

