9.3.3 Covariates

Demographic characteristics and cohort entry information:

Sex

NIS Protocol Page 26 of 48 BI Study Number: 1237-0110 c38660249-01

Proprietary confidential information © 2022 Boehringer Ingelheim International GmbH or one or more of its affiliated

- Age
- Calendar year of cohort entry
- Season of index date (winter, spring, summer, fall)

Additional, the following clinical characteristics will be measured during the 1 year pre-index baseline period:

Previous COPD treatments

- ➤ LAMA monotherapy
- ➤ LABA monotherapy
- > ICS monotherapy
- ➤ LAMA/ICS combination therapy

Use of other respiratory drugs

- Mucolytics
- > Theophylline
- ➤ Short-acting beta-agonists
- > Short-acting muscarinic antagonists
- Previous acute COPD exacerbation (measured both 12 months and in the 30 days prior to cohort entry), categorized as 0, 1 or 2+.
 - ➤ All exacerbations (Moderate+Severe)
 - An outpatient visit with a diagnosis code for COPD in any field + a prescription for an oral corticosteroid or an antibiotic for respiratory infections (Moderate)
 - ➤ Hospitalizations or emergency room visits with a primary diagnosis for COPD (Severe)
- Hospitalizations caused by exacerbation of COPD in 12 months prior to the index date:
 - **>** 0;
 - **>** 1;
 - **>** 2+;
- all-cause hospitalizations in 12 months prior to index date:
 - > 0;
 - **>** 1;
 - **>** 2+;
- Comorbidities:
 - > Cardiovascular disease
 - > Cerebrovascular disease
 - Diabetes
 - > Chronic kidney disease
 - > Pneumonia
 - > Cancer
 - Cirrhosis

NIS Protocol Page 27 of 48 BI Study Number: 1237-0110 c38660249-01

Proprietary confidential information © 2022 Boehringer Ingelheim International GmbH or one or more of its affiliated

- Charlson Comorbidity Index (CCI)
- History of medications dispensed in the 12 months before or on the index date will be identified from the pharmacy dispensing history:
 - > Cardiovascular drugs:

Antihypertensives

Antiarrhythmics

Nitrates

heart failure medications

- ➤ Lipid-lowering medications
- ➤ Blood glucose-lowering medications
- ➤ Anticoagulants and antiplatelet agents
- > Antibiotics
- ➤ Antineoplastic agents

COPD severity

The definition of the severity of COPD in this study was developed based on the information in previous studies, GOLD recommendations and clinical practice in Taiwan, see below. Patients who fulfil criteria for more than one category will be classified as being in the most severe category.

Criteria of COPD severity:

➤ Mild:

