### 7.3 COVARIATES

Demographic characteristics and cohort entry information:

- Sex
- Age
- Calendar year of cohort entry
- Season of index date (winter, Dec-Feb; spring, Mar-May; summer, Jun-Aug; fall, Sep-Nov )

Additional characteristics will be defined during the 1-year pre-index baseline period:

- Previous COPD treatments
  - LAMA monotherapy
  - LABA monotherapy
  - ICS monotherapy
  - LAMA/ICS free combination therapy
- Use of other respiratory drugs
  - Mucolytics
  - Theophylline
  - Short-acting beta-agonists
  - Short-acting muscarinic antagonists
- Previous acute COPD exacerbation (measured both 12 months and in the 30 days prior to cohort entry), categorized as 0, 1, or 2+.
  - All exacerbations (Moderate+Severe)
  - An outpatient visit with a diagnosis code for COPD in any field + a prescription for an oral corticosteroid or an antibiotic for respiratory infections (Moderate); prescriptions within 30 days of each other were considered as continuation of the initial exacerbation.
  - Hospitalizations or emergency room visits with a primary diagnosis for COPD

(Severe); hospitalizations or emergency room visits within 30 days of each other were considered as continuation of the initial exacerbation.

- Hospitalizations caused by exacerbation of heart failure in 12 months prior to index date, categorized as
  - 0;
  - 1;
  - 2+.
- All-cause hospitalizations in 12 months prior to index date;
  - 0;
  - 1;
  - 2+.
- Comorbidities:
  - Cardiovascular disease
  - Cerebrovascular disease
  - Diabetes
  - Chronic kidney disease
  - Pneumonia
  - Cancer
  - Cirrhosis
- Charlson Comorbidity Index (CCI)
- History of medications dispensed in the 12 months before or on the index date will be identified from the pharmacy dispensing history:
  - Cardiovascular drugs:
    - antihypertensives;
    - antiarrhythmics;
    - nitrates;
    - heart failure medications
  - Lipid-lowering medications
  - Blood glucose-lowering medications
  - Anticoagulants and antiplatelet agents
  - Antibiotics
  - Antineoplastic agents
- COPD severity

The definition of the severity of COPD in this study was developed based on the information in previous studies, GOLD recommendations and clinical practice in Taiwan, see below. Patients who fulfil criteria for more than one category will be classified as being in the most severe category.

Operational definition of COPD severity:

- Mild:

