## **10. DATA ANALYSIS**

### **10.1 MAIN ANALYSIS**

All variables, including patient characteristics, baseline measures, and outcomes, will be analyzed descriptively.

- For all analyses, variables will be reported as follows: Continuous variables (e.g., age) will be presented as means (with standard deviation, SD) and/or medians (with interquartile range, IQR), minimum, maximum.

- Categorical variables (e.g., sex) will be presented as absolute and relative frequencies.

All analyses will be presented for each treatment group (Tio+Olo vs LABA/ICS) overall. We will first describe formation of the study cohort. Propensity score (PS) matching will be used to generate two comparable treatment groups. All covariates, except season of index date, will be used to estimate the propensity score with logistic regression. Patients in LABA/ICS group will be individually matched to patients in the Tio/Olo group with 1:1 ratio. A caliper of 0.06 standard deviation of logit (propensity score) will be used to define the range of estimated PS within which to select the comparator. Within that range the LABA/ICS patient with the closest estimated propensity score to the Tio/Olo patient will be selected.

Patient characteristics at baseline in patients treated with Tio+Olo and patients treated with LABA/ICS will be described separately using standard descriptive statistics after propensity score matching. Absolute standardized differences (ASDs) will be used to compare the characteristics between the two groups after propensity score matching, in which a  $>0.1$  ASD indicates a meaningful difference.

All the analyses for primary outcome and secondary outcomes will be performed on patients after propensity score matching. Baseline characteristic table shell are provided in [Table 1](#). The propensity score matching will be carried out once without re-matching.

For the analysis of the primary outcome, individuals will be followed up from the index date until the first moderate or severe COPD exacerbation. The data after the earliest date of the following event would be censored:

- 1) disenrollment
- 2) the end of the study period
- 3) death
- 4) discontinuation of index drug use (a lapse of 45 days without subsequent prescription)
- 5) switching from Tio/Olo to ICS/LABA or from ICS/LABA to Tio/Olo
- 6) escalation to triple therapies (ICS/LAMA/LABA free or fix dose combination)

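### Exacerbation and admission history is capped at 2+ in the propensity score and in Table 1, so confounding above two events may remain and would not show; a cheap improvement, low to moderate priority

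*Protocol*

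**What the plan says.** - **Protocol 9.3.3** lists "Previous acute COPD exacerbation (measured both 12 months and in the 30 days prior to cohort entry), categorized as 0, 1 or 2" (the top level being two or more), for all, moderate and severe events. SAP 7.3 repeats this. All-cause admissions have the same three levels.
- **Protocol 9.3.3** also lists "Hospitalizations caused by exacerbation of COPD in 12 months prior to the index date", again as 0, 1, 2+. In the same place SAP 7.3 has "Hospitalizations caused by exacerbation of heart failure in 12 months prior to index date, categorized as" 0, 1 or 2+. The SAP's Table 1 shell has COPD admissions.
- **SAP 10.1**: "All covariates, except season of index date, will be used to estimate the propensity score with logistic regression". Matching is 1:1, done once. The outcome model contains treatment alone unless a baseline covariate has an absolute standardized difference (ASD) above 0.1.
- **SAP Table 1 shell** shows every exacerbation and admission variable as 0, 1, >=2.
- **Protocol section 4**, on who receives the comparator, cites guidance to "initiate ICS/LABA in patients with high blood eosinophils level and frequent exacerbation history". The next sentence says that "ICS containing therapy has been widely used inappropriately in real world practice".

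**The concern.** Exacerbation history is the covariate closest to the primary outcome, and the protocol's rationale names it as a reason for choosing the comparator. With the cap, a patient with 2 prior exacerbations and one with 8 look the same to the score on these variables. If the patient with 8 is more likely to get ICS/LABA, matching leaves more such patients in the ICS/LABA arm and the comparison tilts towards Tio/Olo.

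The plan's safeguards share the cap. The ASD check uses the same three levels, and the SAP's regression adjustment starts only when an ASD exceeds 0.1. Protocol 9.7.1 says other known predictors will enter the Cox model, but SAP 10.1 does not carry this over.

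The 30-day window adds little. SAP 7.3 merges same-type events within 30 days of each other, so a 30-day level of 2+ for moderate or severe events alone can hardly occur.

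At stake are the primary HR and, more so, the annualized exacerbation rate, a secondary outcome in which very frequent exacerbators weigh most.

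**Working it through.** The documents give no distribution of prior counts by arm, so there is no plan figure to reproduce. The size can only be shown under assumptions.

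**1. When does the cap matter?** It matters only if prescribing varies within 2+. With an odds ratio OR per prior event, a patient with 8 events has OR^6 times the odds of ICS/LABA of a patient with 2: 1.05^6 = 1.34, 1.10^6 = 1.77, 1.20^6 = 2.99. If prescribing changes only at two events, this factor is 1 and the cap loses nothing.

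**2. Model (assumed).**
- Each patient's yearly exacerbation rate is gamma distributed, mean 1.0 or 1.3, shape 0.7 or 1.0. The prior count is Poisson given that rate, with 20% of events severe.
- logit P(ICS/LABA) = a + count × ln(OR).
- Matching is exact on 0/1/2+ for moderate, severe and all events. There is no drug effect.
- Null rate ratio = mean rate in Tio/Olo ÷ mean rate in matched ICS/LABA. The Cox HR also assumes a median of 9 months on treatment.

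**3. Results with the cap at 2+ (the true value is 1).**

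| | OR 1.05 | OR 1.10 | OR 1.20 |
|---|---|---|---|
| Rate ratio, mean 1.0 | 0.989 | 0.979 | 0.968 |
| Rate ratio, mean 1.3 | 0.988 | 0.979 | 0.964 |
| Primary HR, mean 1.0 | not run | 0.990 | 0.989 |
| Primary HR, mean 1.3 | not run | 0.994 | 0.989 |

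Crossing both means with both shapes widens the rate ratio to 0.948 to 0.993. Patients at 2+ are 24 to 32% of the cohort and carry 50 to 65% of expected events. With the cap moved to 6+, the rate ratio is within about 0.004 of 1 and the HR is 0.999 to 1.001.

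**4. Threshold prescribing.** With odds doubled at two or more events and flat above that, the null rate ratio is 0.998 to 1.002.

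**5. A second model.** Assume a Tio/Olo mean of 0.8 prior events, an ICS/LABA mean 1.25 to 1.5 times higher, 25% of events severe, and a hazard 11 to 35% higher per prior event. Approximate bias factor on the HR:

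| Coding in the score | Factor |
|---|---|
| Total only, 0/1/2+ | 0.943 to 0.995 |
| Moderate, severe and total, each 0/1/2+ (closest to the SAP) | 0.972 to 0.998 |
| Total 0, 1, 2, 3, 4+ | 0.985 to 0.999 |
| Total 0 to 5, 6+ | 0.997 to 1.000 |

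**6. Effect on the primary test.** From Protocol 9.5 (HR 0.9, two-sided 0.05, 90% power), the events needed are 4(1.960 + 1.282)² / (ln 0.9)² = 3787. A null HR of h shifts the test statistic by √(3787/4) × |ln h|. For h = 0.994 the shift is 0.19 and the false-positive rate is 5.4%. For h = 0.989 the shift is 0.34 and the rate is 6.3%. For h = 0.972, the low end of the SAP-like row in step 5, the shift is 30.77 × 0.0284 = 0.87; the rate at the nearby value 0.97 is 15.5%.

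**7. Would the ASD rule catch it?** In the step 2 model the residual ASD of the total count after matching is 0.009 to 0.051, always below 0.1.

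**The case against.** **The premise is weak.** A reader might infer that the protocol shows ICS/LABA going to frequent exacerbators in these data. It does not. It reports a guideline recommendation that also requires high eosinophils, and then says practice departs from guidance. The cited report is dated 2021, while index dates run from 2014 to 2019. This stands: the amount of channelling is unknown.

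**Frequent need not mean more with each event.** The protocol's own Severe class uses one- and two-event thresholds. If prescribers think the same way, step 4 applies and nothing is lost. This also stands.

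**The score holds more than one three-level variable.** Moderate and severe events are separate, and COPD severity class, oxygen or nebuliser use, respiratory drugs and antibiotics are included. This stands in part. In step 5, separate moderate and severe terms about halve the bias. The Severe class, however, cannot separate 2 events from 8.

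**The effect on the primary outcome is small**, and by the plan's own ASD criterion the cohorts would count as balanced even with counts displayed. Both are true. The second is a reason to change the score and not to rely on the check.

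**Unseen analyses may exist.** The SAP contents list shows redacted sections, and the protocol's ENCePP checklist points to stratified analyses in a section 9.7.2 that the visible text lacks. So one may say only that the visible tables would not show the imbalance.

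**Conclusion.** The cap at 2+ in the score, and the same cap in the balance table, are confirmed by the text. Residual confounding within 2+ is possible and would go unseen in the visible tables. That it is present is not established, and the stronger statement that confounding by indication remains should not be made.

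If the odds of ICS/LABA rise by 5 to 20% per prior event throughout, the null annualized exacerbation rate ratio is about 0.95 to 0.99. For 10 to 20% per event the primary HR is off by about 1%, against a design effect of 10%. Both favour Tio/Olo. The stronger assumptions of step 5 reach 0.972 on the HR. With threshold prescribing there is no bias. These are upper figures for the assumed channelling, because other covariates would absorb part of it.

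Finer counts would do nothing about eosinophils, the other half of the cited recommendation, which are not a listed covariate.

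This is a cheap improvement of low to moderate priority.

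**What to change.** 1. **Reconcile first.** Settle whether the admission covariate is COPD (Protocol 9.3.3, Table 1 shell) or heart failure (SAP 7.3).
2. **Change the score.** In SAP 7.3 and 10.1, enter the 12-month numbers of moderate exacerbations, severe exacerbations, COPD admissions and all-cause admissions in finer form, for example 0, 1, 2, 3, 4, 5, 6+ or log(1 + count). This is the step that acts.
3. **Show the counts.** Add the mean and SD of each count by arm to Table 1, and keep the 0, 1, >=2 rows. Treat this as transparency. The ASD > 0.1 rule should not be relied on to trigger adjustment, since the residual ASD would be about 0.01 to 0.05.

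The cost is SAP wording and a few more model terms. The counts must already be computed to form the levels, so no new data are needed. A few very frequent exacerbators may lose a match within the caliper.
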